### ***Relationship of AE to Study***

The relationship of each adverse event (AE) to the study procedures will be characterized. The PI will make this determination and will classify AEs as related or unrelated. “Related” will mean that there is a reasonable possibility that the AE may be related to the study agent(s). “Not Related” will mean that there is not a reasonable possibility that the AE is related to the study agent(s). When a SAE is assessed as “not related” to study agent(s), an alternative etiology, diagnosis, or explanation for the SAE should be provided. If new information becomes available, the relationship assessment of any AE should be reviewed again and

updated, as required. The study drug (pravastatin) and standard-of-care regimen, Rifafour (isoniazid, rifampin, pyrazinamide, ethambutol) will be assessed for relationship with the AE.

### ***Reporting of Serious Adverse Events, and Unanticipated Problems***

Requirements, definitions and methods for expedited reporting of adverse events are outlined in Version 2.0 of the DAIDS EAE Manual, which is available on the DAIDS RSC website at: <https://rsc.niaid.nih.gov/clinical-research-sites/manual-expedited-reporting-adverse-events-dais>. This study will use the SAE form of expedited adverse event reporting, as defined in Version 2.0 of the DAIDS EAE Manual. Expedited reporting is required for the study drug (pravastatin) and the standard-of-care regimen, Rifafour (isoniazid, rifampin, pyrazinamide, ethambutol). The EAE reporting period for this study will be 30 days, which is the day of the final study visit. During these 30 days, all SAEs will be reported to DAIDS in an expedited fashion, within 3 days of occurrence, in accordance with DAIDS EAE Manual. Any of the study and non-study drugs which a participant has taken will be assessed for relationship with the SAE.

After the protocol-defined EAE reporting period, unless otherwise noted, only SUSARs as defined in Version 2.0 of the DAIDS EAE Manual will be reported to DAIDS if the study staff become aware of the events on a passive basis (from publicly available information).

The DAIDS Adverse Experience Reporting System (DAERS), an internet-based reporting system, must be used for EAE reporting to DAIDS. In the event of system outages or technical difficulties, EAEs will be submitted using the DAIDS EAE Form. This form is available on the DAIDS RSC website at <https://rsc.niaid.nih.gov/clinical-research-sites/paper-eae-reporting>

**For questions about DAERS, please contact NIAID CRMS Support at [[contact]](mailto:[contact]). Please note that site queries may also be sent from within the DAERS application itself.**

**For questions about expedited reporting, please contact the DAIDS RSC Safety Office at [[contact]](mailto:[contact]).**

All AEs will be graded using the Division of AIDS table for Grading Severity of Adult and Pediatric Adverse Events, Corrected Version 2.1, July 2017. The clinical course of each event will be followed until resolution, stabilization, or until it has been determined that the study intervention or participation is not the cause. Serious AEs that are still ongoing at the end of the study period will be followed up to determine the final outcome. Any serious AE which we become aware of through a passive basis (participant reporting back to the study team, or through publicly available information), which occurs after the study period (after day 30) and is considered to be possibly related to the study intervention (suspected, unexpected serious adverse reactions, or SUSARs) or study participation will be recorded and reported immediately.

### ***Association and Attribution/causality***

An adverse event is considered associated with the use of the drug (Adverse Drug Reaction) if the attribution is possible, probable or definite.

The following definitions for rating attribution/causality will be:

Relatedness Rating	Definition
Not Related	There is not a reasonable possibility that the AE is related to the study agent (pravastatin) or Rifafour (isoniazid, rifampin, pyrazinamide, ethambutol)

Related	There is a reasonable possibility that the AE may be related to the study agent (pravastatin) or one or more components of Rifafour (isoniazid, rifampin, pyrazinamide and ethambutol)
---------	--

### ***Severity\****

With the exception of creatinine kinase elevation, all symptoms and laboratory findings will be graded according to severity using the Division of AIDS Table for Grading Severity of Adult and Pediatric Adverse Events, Corrected Version 2.1, July 2017, which, in our view is the most comprehensive grading scale for patients with infectious diseases, including TB or HIV.

The protocol-specific criteria for grading elevated CK are as follows:

PARAMETER	GRADE 1 MILD	GRADE 2 MODERATE	GRADE 3 SEVERE	GRADE 4 POTENTIALLY LIFE-THREATENING
Creatinine kinase, high	3 to < 6 x ULN	6 to < 10 x ULN	10 to < 20 x ULN	> 20 x ULN

The DAIDS toxicity table criteria for grading liver function tests are as follows:

PARAMETER	GRADE 1 MILD	GRADE 2 MODERATE	GRADE 3 SEVERE	GRADE 4 POTENTIALLY LIFE-THREATENING
AST or SGOT, High	1.25 to < 2.5 x ULN	2.5 to < 5.0 x ULN	5.0 to < 10.0 x ULN	≥ 10.0 x ULN
ALT or SGPT, High	1.25 to < 2.5 x ULN	2.5 to < 5.0 x ULN	5.0 to < 10.0 x ULN	≥ 10.0 x ULN
Total bilirubin	1.1 to < 1.6 x ULN	1.6 to < 2.6 x ULN	2.6 to < 5.0 x ULN	≥ 5.0 x ULN

\*The DAIDS AE Grading Table is available at: <https://rsc.niaid.nih.gov/clinical-research-sites/daids-adverse-event-grading-tables>.

### ***Reporting***

**AE:** Adverse events (AE) will be collected by the Investigators from the time a study participant receives the first dose of study drug through the Day 30 study visit. Any AE (serious or non-serious) observed by the Investigator or reported by the study participant that meets the AE reporting requirements (see below) will be recorded on an Adverse Event Case Report Form. The Investigator will review each AE and assess its relationship to drug treatment based on all available information at the time of the completion of the case report form. The following information will be recorded for each AE reported:

- Diagnosis of the AE, if possible. In the case where an overall diagnosis cannot be made, each specific sign and/or symptom will be recorded as individual AEs;
- Date of onset;
- Stop Date (duration) if applicable;
- Severity;

- Action taken with study drugs;
- Other action taken;
- Outcome;
- Relationship to study drugs;
- Seriousness.

The following adverse events must be reported on an Adverse Event Report Form:

- New medical diagnosis (at the time of enrollment, if the patient already has a medical diagnosis whose signs or symptoms worsen during the study to a Grade 3 or 4, this is an adverse event that must be reported)
- Any grade 3 or higher adverse event
- Study drug discontinuation due to an adverse event
- Pregnancy
- Lab values that are considered clinically significant by the investigator

The standard-of-care drugs are Rifafour (Ethambutol, Isoniazid, Rifampin, and Pyrazinamide) and the study drug is pravastatin. The most common adverse effects associated with the standard-of-care drugs and the study drug are specified in the "[Study Drugs](#)" section. The Investigator is responsible for monitoring all adverse events that are observed or reported during the study, regardless of whether they are related to the study drug. Participants presenting with AEs to other facilities during the study period will be referred back to the study site in order to complete all study visits and data collection. The participant will be given instructions to notify the study team if any AEs develop following the study period.

In accordance with the FDA's Code of Federal Regulations, the study Sponsor and the participating Investigators are responsible for reviewing all information relevant to the safety of the study drug and standard-of-care therapy. Reporting and monitoring of SAEs is required to alert the FDA, Sponsor, institutional review boards, and the clinical Investigators of real and potential safety issues. The Investigators will carefully review the AE Reports and use this information to monitor the investigational drug's toxicity profile and patient safety. Any AE associated with the use of the study drug and/or the standard of care regimen that is both serious and unexpected will be reported to the FDA in the form of a written Safety Report.

The responsible institutional review boards, FDA and South African Regulatory body South African Health Products Regulatory Authority will be notified of all SAEs and AEs according to their individual guidelines.

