### ***Safety and Tolerability Endpoints***

The primary endpoint for analysis of safety and tolerability is Grade 3 or higher adverse events. Secondary endpoints include permanent discontinuation of assigned study regimen for any reason (other than new recognition of participant ineligibility based on absence of *M. tuberculosis* growth in baseline sputum cultures, or growth of *M. tuberculosis* resistant to rifampin by GeneXpert. Other aspects of safety and tolerability that will be assessed include mortality and the rates and types of toxicity thought related to study drugs by the Investigator.

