## **5. Adverse Events**

The Investigators are responsible for eliciting adverse events by observing study participants and recording all adverse events observed by him/her or reported by study participants during the trial.

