#### Other toxicities

Grade 1 toxicities: In general, for grade 1 toxicities, the patient will be followed carefully, and the study drugs will be continued.

Grade 2 toxicities: For grade 2 toxicities, the patient will be followed more carefully, with additional laboratory and/or clinic visits as necessary, and the study drugs temporarily held at the investigator's discretion.

Grade 3 toxicities: For any grade 3 toxicity involving creatinine kinase elevation, with or without myopathy, myalgias, hepatitis, nausea/vomiting, and/or diarrhea, that, in the principal investigator's judgment is due to study drug, the study drug will be discontinued. The clinician should rule out other possible causes of the symptoms before discontinuing study medication. When possible, concomitant medications should be held first at the discretion of the principal investigator if he/she suspects they are contributing to the toxicity. In the event of study product discontinuation, management of the standard of care TB drugs will revert to the site clinician as per local practice.

Grade 4 toxicities: Any patient with grade 4 renal, hepatic, cardiac or hematological toxicity will be immediately discontinued from study therapy. The laboratory test or clinical finding in question will be reassessed as soon as possible. The repeat test will guide management of the event as follows:

- If the repeat assessment shows toxicity of grade 3 or lower, and if the patient has continued to receive study drugs between the two testing dates, then the patient will be managed according to the appropriate toxicity level of the repeat test.
- If the repeat test shows toxicity of grade 3 or lower, and if the participant has not received study drugs between the two testing dates, then the participant will be managed at the discretion of the investigator with regard to the re-administration of study drugs, and otherwise according to the toxicity level of the repeat test.
- If the repeat test shows grade 4 toxicity, then the participant will be permanently discontinued from study medications. Further treatment of TB will be directed by the investigator on an individualized basis. The participant will continue to be followed for study monitoring purposes (as are other participants who make a permanent departure).

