For other grade 4 toxicities, the study drugs will be permanently discontinued. Toxicities graded 3 or 4 and occurring during study therapy will be documented on the AE Form, according to the criteria described in the following sections. The maximum level of toxicity reached will be clearly indicated.

For all toxicities that are treatment-emergent and that require permanent discontinuation of study treatment, relevant clinical and laboratory tests will be obtained as clinically indicated and repeated as needed until final resolution or stabilization of the toxicity.

**Permanent discontinuation of study drugs:** Certain events or conditions may necessitate permanent discontinuation of the statin study drug. Participants who experience such events or conditions, however, will still be "on study" and will be followed until study completion. Study drug will be discontinued with continued study follow-up for participants in whom treatment-emergent drug toxicity warrants discontinuation of study therapy and for participants who become pregnant. If study drug is permanently

discontinued, continued standard-of-care therapy for tuberculosis may be administered at the investigator's discretion. If Rifafour is discontinued, the individual components (isoniazid, rifampin, pyrazinamide, and ethambutol) may be gradually re-introduced, as per national guidelines.

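### Related toxicity is to be assessed at any grade, but the AE form does not require grade 1-2 symptoms or temporary holds, and no other form is named for them

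*Combined protocol and SAP*

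**What the plan says.** Several parts of the protocol ask for adverse events without a grade limit. Safety and Tolerability Endpoints (section 4) lists, after the primary and secondary endpoints, "the rates and types of toxicity thought related to study drugs by the Investigator". The opening of section 5 makes investigators responsible for "recording all adverse events observed by him/her or reported by study participants during the trial". Relationship of AE to Study requires each AE to be attributed, and Severity requires all symptoms and laboratory findings to be graded.

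The Reporting subsection then sets an entry condition for the AE form. An AE "that meets the AE reporting requirements (see below) will be recorded on an Adverse Event Case Report Form", and five kinds of event meet the requirements: a new medical diagnosis, "Any grade 3 or higher adverse event", study drug discontinuation due to an AE, pregnancy, and laboratory values that the investigator judges clinically significant. For each AE so reported, the form takes onset, stop date, severity, action taken with study drug, outcome, relationship and seriousness.

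Other toxicities adds: "Toxicities graded 3 or 4 and occurring during study therapy will be documented on the AE Form". For grade 2 toxicities it provides for closer follow-up, "with additional laboratory and/or clinic visits as necessary, and the study drugs temporarily held at the investigator's discretion".

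**The concern.** Relatedness by itself does not put an event on the AE form. A grade 1-2 nausea, headache or muscle ache attributed to pravastatin meets none of the five conditions unless it amounts to a new diagnosis or leads to discontinuation. A temporary hold is not named either.

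This is a tolerability and dose-selection study with 5 to 10 participants per arm. In arms of that size, related events below grade 3 and dose interruptions are likely to be much of what can be observed. Data Analysis (section 18) also plans a model of exposure against outcomes such as safety and tolerability. If relationship, dates and action taken are not captured in one place for lower-grade symptoms, the rates of related toxicity cannot be tabulated reliably by grade and arm, and the model has incomplete data below grade 3.

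**Working it through.** The plan states no figure that depends on this point, so the check is mainly a comparison of texts.

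1. **What the measure needs.** A rate of related toxicity by type needs, for each event, its type, grade and relationship. To speak to tolerability it also needs onset, stop date and what was done with the drug.

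2. **Where those items are held.** The AE form holds all of them. Targeted symptom assessment asks about 15 listed symptoms and has other symptoms recorded and graded. Section 9 adds a symptom checklist kept in the source document, and Data Capture Methods has visit data entered in the database. None of these is said to hold relationship, dates or action taken. Appendix 1 schedules the targeted assessment at screening, Days 1, 7, 15, 21 and 30, and unscheduled visits. AE assessment is daily on Days 1-15 and again on Days 21 and 30. Muscle pain is not among the 15 prompted symptoms, so mild myalgia would surface only through the open question or the AE assessment.

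3. **Test cases against the five conditions.**
   - Grade 1 nausea, judged related, drug continued: form not required.
   - Grade 2 muscle pain, judged related, drug temporarily held: unclear. The condition is discontinuation, without the word permanent, and the grade 4 rule under Other toxicities uses discontinued for a stop that may be followed by re-administration.
   - Grade 2 symptom leading to discontinuation: form required.
   - Grade 2 CK or ALT: available from the laboratory data, and on the form if judged clinically significant.
   - Any grade 3 event: form required.

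4. **What is not affected.** "The primary endpoint for analysis of safety and tolerability is Grade 3 or higher adverse events", and all such events reach the form. So do the events behind the discontinuation and grade 3+ criteria in Data Analysis and the decision table. Symptomatic ALT above 3 times ULN, which can be grade 2 and counts against escalation, leads to permanent discontinuation under Liver toxicity and so reaches the form too. CK and liver tests are scheduled on Days 7, 15, 21 and 30 and can be tabulated at any grade.

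5. **Size, illustrative only.**
   - Assume that 10-30% of participants have a related grade 1-2 symptom. Expected number in an arm of 10: 10 × 0.10 = 1 to 10 × 0.30 = 3. Chance that such an arm has at least one: 1 − 0.90^10 = 0.65 to 1 − 0.70^10 = 0.97.
   - For comparison, the pravastatin Tolerability section gives CK above 10 times ULN in 4 of 464 patients on 80 mg: 4/464 = 0.0086. At that risk, the chance of no such event in 10 participants is (1 − 4/464)^10 = 0.92. That rate comes from a mean of 8.6 months of exposure, against about two weeks here, and covers one laboratory event.

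**The case against.** The strongest reply is that the list limits the form and not the collection of AEs. A reader might infer that lower-grade events are not collected, leave no analysable record, or would lead to a dose being reported as free of related toxicity. The documents do not support any of these. All AEs are to be recorded, each is to be attributed, all symptoms are to be graded, a checklist is kept in source, and visit data go into the database. The layout of the source documents and the Data Management Operations Manual are not before us and may provide the missing fields. Three of the five conditions (new diagnosis, discontinuation and significant laboratory values) can apply at grade 1-2. The grade 3-4 sentence under Other toxicities does not say that only those grades are documented. Doses are directly observed and checked against a treatment card, so an interruption leaves a trace.

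All of that stands. It leaves a general duty to record and attribute every AE, alongside a form that admits only some, with no other form named for relationship, dates and action taken. A treatment card shows that a dose was not taken, but is not said to show why. Section 9 treats missing more than 2 doses as non-compliance and does not say whether a hold directed by the investigator counts.

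A second objection concerns burden. A form entry for every AE related to Rifafour would bring in expected effects: the protocol cites hyperuricemia in up to 66% on pyrazinamide and aminotransferase elevation in 10-20% on isoniazid. That is right, and the added trigger should be limited accordingly.

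**Conclusion.** The point holds as a gap between sections. Related toxicity is to be assessed at any grade, yet the one form named for relationship, dates and action taken does not require grade 1-2 symptoms and does not name temporary holds. The related-toxicity measure, and the exposure-tolerability model so far as it uses such events, would rest on incomplete data below grade 3. The measure stands among the other safety aspects, so the primary endpoint and the escalation decisions are untouched, as are CK and liver test results.

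The size cannot be derived from the documents. One to 3 participants in an arm of 10 rests on the assumed 10-30% symptom rate, and the 0.92 for CK is illustrative only. The conclusion also assumes that no operational document outside the protocol already assigns these fields. The change is worth making before enrolment, but the trial does not fail without it.

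**What to change.** In Reporting (section 5), add two conditions for the AE form: (i) any symptomatic AE of any grade judged related to pravastatin, and (ii) any AE leading to a temporary hold of study drug. Bring the documentation sentence in Other toxicities into line, and report related AEs by grade and arm. Leave the grade 3+ primary endpoint and the escalation rule as they are.

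Limiting (i) to symptoms and to pravastatin keeps routine laboratory changes and expected Rifafour effects off the form. It requires relationship to pravastatin to be rated separately, because the relatedness table defines one rating for pravastatin or Rifafour together. The endpoint text should then say that related symptoms below grade 3 are reported for pravastatin.

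If the sponsor prefers not to widen the form, the minimum is to restrict the related-toxicity measure to reportable AEs, or to name the document that holds relationship, dates and action taken for the rest.

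The cost is protocol and form wording plus a few more entries per participant. At the assumed 10-30%, trigger (i) would concern 35 × 0.10 = 3.5 to 35 × 0.30 = 10.5 of at most 35 evaluable participants. No visits are added, since AEs are already assessed daily through Day 15 and on Days 21 and 30.

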***Targeted symptom assessment***

Participants will be asked whether they have experienced any of the following since the last study visit: fevers, sweats, cough, rash, itching, jaundice, nausea, vomiting, diarrhea, loss of appetite, vision problems, numbness/tingling of extremities, headache, joint pain, eye pain. In addition, patients will be asked whether they have had other symptoms (not listed above); if yes, then these symptoms will be recorded and graded. In addition, targeted diagnostic evaluations may be indicated to determine the underlying cause of symptoms and their association with study drug use.

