#### Creatinine Kinase Elevation

For Grade 1 (3 to  $< 6 \times$  ULN) or Grade 2 (6 to  $< 10 \times$  ULN) creatinine kinase elevation, participants may continue study drug treatment and should be carefully evaluated and followed closely. For Grade 3 (10 to  $< 20 \times$  ULN) or higher creatinine kinase elevation, participants will permanently discontinue statin but will be requested to attend follow-up visits until study end.

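### Low-grade CK, liver and muscle events have no assured route onto the AE form, so the planned rates of drug-related toxicity would be incomplete below grade 3

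*Combined protocol and SAP*

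**What the plan says.** Section 4, Safety and Tolerability Endpoints, states: "The primary endpoint for analysis of safety and tolerability is Grade 3 or higher adverse events". Among other aspects to be assessed it names the "rates and types of toxicity thought related to study drugs by the Investigator", with no grade limit.

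Section 5 opens by making investigators responsible for eliciting AEs and for recording all that they observe or are told of. Reporting then narrows this: an AE "that meets the AE reporting requirements (see below) will be recorded on an Adverse Event Case Report Form". The listed requirements are a new diagnosis, any event of grade 3 or higher, stopping study drug because of an AE, pregnancy, and "Lab values that are considered clinically significant by the investigator". Severity and relationship to study drugs are among the items recorded for each AE reported this way. Other toxicities adds: "Toxicities graded 3 or 4 and occurring during study therapy will be documented on the AE Form".

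Below grade 3, the plan manages individuals. For grade 1 or 2 CK, "participants may continue study drug treatment and should be carefully evaluated and followed closely". For grade 2 toxicities in general, follow-up is intensified "and the study drugs temporarily held" if the investigator so chooses.

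The Targeted symptom assessment list ends "numbness/tingling of extremities, headache, joint pain, eye pain". Muscle pain and weakness are not on it. A catch-all question follows, and symptoms it brings out are recorded and graded.

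**The concern.** Safety and tolerability is a primary endpoint, and section 2 says the findings are to inform dose choice for a larger study. The characteristic statin effects are on CK, liver tests and muscle. With 5 to 10 participants per arm, much of the information on them is likely to lie below grade 3. If low-grade events reach the AE form only when an investigator chooses to enter them, the rate of related toxicity has no complete numerator below grade 3. An arm could include participants with CK of 3 to <10 x ULN, or with doses held for grade 2 myalgia, and still show no related toxicity on the forms. The trial is open-label (section 18, Recruitment strategy), so the person exercising that discretion knows the dose.

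The Early stopping rules text also asks the DSMB to weigh the frequency and severity of AEs against what is known in cardiovascular patients, again with no grade limit. AE forms filtered largely at grade 3 are a weak basis for that comparison.

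**Working it through.** The plan gives no figure for this point, so the main check is to set its rules side by side.

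**1. What reaches the form below grade 3.** Grade limits are from section 5, Severity; management is from the sections that follow it.

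| Finding | Range or grade | Management | Assured entry on AE form? |
|---|---|---|---|
| CK | 3 to <10 x ULN | drug may continue, close follow-up | No; only if judged clinically significant |
| ALT, AST | 1.25 to <5 x ULN | drug stopped if ALT >3 x ULN with hepatitis symptoms or with bilirubin at least 2 x ULN | Only where drug is stopped; otherwise if judged clinically significant |
| Total bilirubin | 1.1 to <2.6 x ULN | general grade 1-2 rules | As for ALT and AST |
| Muscle symptoms | grade 1-2 | general grade 1-2 rules | Only as a new diagnosis or a discontinuation |
| Temporary hold | grade 2 | investigator's discretion | No; discontinuation is listed, a hold is not |

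**2. Where relatedness is recorded.** Reporting has the investigator judge relationship when completing the case report form. Relationship of AE to Study asks for a classification of each AE but names no other record for it. A low-grade event that is not on the form therefore has no stated place for its attribution.

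**3. The conflict.** The opening of section 5 requires all AEs to be recorded, while Reporting restricts the form to five categories. A site could follow either rule and believe it was compliant.

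**4. The symptom prompt.** Joint pain and eye pain are asked about by name. Muscle pain and weakness depend on the participant answering the catch-all, although the section 18 escalation rule counts musculoskeletal events.

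**5. Size.** Two rates in section 13 give limited context. Both come from other settings and exposure times, so applying them here is an assumption.

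- CK >10 x ULN at 80 mg: 4/464 = 0.86%, over a mean of 8.6 months. The chance of at least one case is 1 − (1 − 0.0086)^10 = 8.3% in an arm of 10, and 1 − (1 − 0.0086)^35 = 26% in 35. At that rate most arms would have no grade 3+ CK event. An observed 0 of 10 still leaves a two-sided 95% upper limit of 1 − 0.025^(1/10) = 31%.
- Asymptomatic aminotransferase elevation on isoniazid: 10-20%. This gives 10 × 0.10 = 1 to 10 × 0.20 = 2 expected per arm of 10, and 3.5 to 7 in 35. The chance of at least one in an arm of 10 is 1 − 0.9^10 = 65% to 1 − 0.8^10 = 89%. The documents give no grade split and no time window. Every arm receives isoniazid, so this shows only that such values should be expected; it says nothing about pravastatin dose.

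**The case against.** The strongest reply is that the data are recorded anyway. Section 5 opens by requiring that all AEs be recorded. The Severity text has symptoms and laboratory findings graded. Section 9 has new symptoms noted in the source document from a standard checklist at each visit, and section 10 has visit data entered in the database. CK and liver tests are taken from everyone at screening and on Days 7, 15, 21 and 30. The catch-all question means that volunteered myalgia is recorded and graded.

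Much of this stands. The laboratory values are not lost, and a table of them could be made at any time. What the reply does not supply is a stated place for severity and relationship of low-grade events outside the form, or a way to reconcile the two recording rules. A catch-all is also weaker than a direct question about the symptom of most interest.

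The reply is right too that no stated decision rule is touched. Grade 3+ events are fully reportable. Where the escalation rule reaches below grade 3, as with ALT >3 x ULN with symptoms or raised bilirubin, the same finding requires permanent discontinuation and so enters the form by that route.

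A reader might infer that most low-grade effects will go unreported, or that reporting will differ between doses. The documents support neither: nobody can say how many low-grade values an investigator would call clinically significant, and unblinded discretion makes differential reporting possible without showing that it will happen. Nor does the plan promise toxicity rates by dose. That is a natural use in a dose-finding study, but section 4 does not say it.

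**Conclusion.** The point holds in a limited form. Below grade 3, CK, liver-test and muscle events and temporary holds have no assured entry on the AE form, where relationship to drug is recorded. The planned rates of related toxicity, which carry no grade limit, would be incomplete there and would rest on an unblinded investigator's judgement. The form criteria conflict with the general duty to record all AEs, and the checklist does not ask about muscle pain or weakness.

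The shortfall cannot be quantified, because the documents give neither a distribution of low-grade CK values nor a rule for clinical significance. The figures under the check are context on borrowed rates. The conclusion rests on the text alone and assumes that sites follow the Reporting list as the specific rule.

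It would be wrong to infer that the primary endpoint or dose escalation is compromised, or that the CK and liver data are missing. The lack of a by-arm laboratory table in section 18 is missing detail in the analysis plan, since the values exist. The attribution gap and the missing muscle prompt are the parts that should be corrected before enrolment, because they are hard to repair afterwards.

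**What to change.** (a) Add muscle pain and muscle weakness to the Targeted symptom assessment list.

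(b) Reconcile Reporting with the opening of section 5. Also require on the AE form, with severity and relationship:
- post-baseline CK of grade 1 or higher;
- post-baseline ALT, AST or bilirubin of grade 2 or higher;
- muscle symptoms of any grade;
- any AE leading to a temporary hold.

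(c) As a descriptive addition to section 18, tabulate worst post-baseline grade against baseline grade for CK, ALT, AST and bilirubin by arm, for each DSMB cohort review. Use all laboratory values regardless of attribution, and include participants who were replaced under section 9. The baseline comparison matters because entry is allowed with bilirubin up to 2 x ULN, while grade 2 starts at 1.6 x ULN.

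The cost is two checklist items, some extra AE forms and one table. No new tests or visits are needed, and the primary endpoint and escalation rules stay as they are. In reading the table, remember that liver-test changes also reflect Rifafour, and that arms are recruited in sequence, so dose is confounded with enrolment period.
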